5.6.1 Unmasking Treatment

A patient's treatment assignment will not be unmasked for the investigator or study site staff until the EOS unless medical treatment of the patient depends on knowing the study treatment the patient received. In the rare event that unmasking is needed because of a

medical emergency, the investigator may unmask an individual patient through the IWRS. Reasons for treatment unmasking must be clearly explained and justified in the eCRF. The date on which the code was broken together with the identity of the person responsible must also be documented.

Patients who are unmasked will be allowed to continue their participation in the study; however, their data may be excluded from per-protocol analyses.

5.7 Treatment Compliance

Patient compliance will be determined from [REDACTED] according to the SOA (Table 6-1). The M/N and MD/E [REDACTED] will [REDACTED] separately. The calculations for determining percentage compliance is presented in Section 7.7.5.2.

At each visit during the treatment period, study site staff will remind the patient of the need to administer the ophthalmic drops as instructed.

Before each visit (Visit 4 through Visit 10), study site staff will call patients to remind them to bring all study drug [REDACTED] to the study site for their visit.

5.8 Prior and Concomitant Therapy

At screening, the following prior therapies will be recorded in the eCRF:

- History of prior study eye surgical procedures
- All medications used within the previous 30 days
- All surgical procedures within the previous 30 days (any body part)

At screening, all patients' prior medications used and surgical procedures undergone within the previous 30 days will be recorded in the eCRF. A history of all prior study eye surgeries must be obtained and recorded (note exclusion criteria 3 and 4, Section 4.1.2).

Use of all concomitant medications will be recorded in the patient's eCRF. The minimum requirement is that drug name and the dates of administration are to be recorded. This will include all prescription drugs, herbal products, vitamins, minerals, and over-the-counter

medications. Any changes in concomitant medications also will be recorded in the patient's eCRF.

All patients' surgical procedures undergone concomitantly during the study must be reported and recorded in the eCRF.

Any concomitant medication or surgical procedure deemed necessary for the welfare of the patient during the study may be given at the discretion of the investigator. However, it is the responsibility of the investigator to ensure that details regarding the medication and surgical treatment are recorded in full in the eCRF.

5.8.1 Descemetorhexis of the Study Eye

As a condition of participating in the study, each patient will undergo descemetorhexis of the investigator-selected study eye at Visit 2 (Day –1). See Section 6.1.2 for details.

In the absence of suitable local guidance or personal preference of the investigator, recommended post-descemetorhexis concomitant therapy consists [REDACTED] [REDACTED] instilled [REDACTED] and [REDACTED] instilled [REDACTED]. However, an investigator will be able to add [REDACTED] dosing after [REDACTED] if the investigator judges it necessary. When more than 1 different eye drop is administered (including study drug), the study drug must be administered first, followed by any non-study eye drop(s) after at least 5 minutes have passed (Section 5.2).

A patient must not be randomly assigned to study drug unless the excised diameter satisfies inclusion criterion 5 (Section 4.1.1).

5.8.2 Rescue Surgical Procedures

Penetrating keratoplasty or endothelial keratoplasty may be offered as rescue surgical procedures to an enrolled patient if the investigator judges that endothelial healing is not complete at Week 12 (Visit 9), or earlier if the investigator considers that the patient needs urgent treatment. If the rescue surgery is performed, the dosing with study drug must be

discontinued immediately (without tapering) and the patient will attend all planned study visits including the follow-up period.

5.8.3 Prohibited and Restricted Concomitant Therapy

5.8.3.1 Prohibited and Restricted Surgical Intervention

Throughout the study, study eyes must not undergo any surgical intervention other than the descemetorhexis at Visit 2. Non-study eyes must not undergo any surgical treatment for FECD or cataract in the screening or treatment periods, but they can be surgically treated during the follow-up period. The non-study eye will not be eligible for participation in the trial, except if the descemetorhexis fails on the first-selected study eye and that eye is not eligible to participate. In that case, if all other inclusion and exclusion criteria are met by the second eye and more than 30 days have passed since the first study descemetorhexis, then the patient can be enrolled using the second eye to qualify.

Punctal occlusion plugs are considered to be surgical interventions.

5.8.3.2 Prohibited and Restricted Medication

The following medications and drugs identified as exclusion criteria are prohibited for use by patients throughout the study:

- Netarsudil or other ROCK inhibitors
- Eye drops and ointments containing 5% sodium chloride
- Devices to improve any ocular symptoms (eg, TrueTear®, LipiFlow®, etc)
- Drugs of abuse (opiates, methadone, cocaine, amphetamines, barbiturates, or benzodiazepines) or more than 2 standard drinks of alcohol per day. Subjects in countries which have lower thresholds for alcohol intake must follow their country's own recommendations and limits for alcohol consumption.
- Contact lenses (except non-study eye)

- Any ophthalmic solution besides artificial tears, over-the-counter anti-allergic ophthalmic products, study drug, or drugs prescribed by the investigator for treatment of the underlying condition
- Any investigational drug besides study drug

6 Study Assessments and Procedures

Before performing any study procedures, all potential patients will sign an informed consent form (ICF). Patients will have the opportunity to have any questions answered before signing the ICF. The investigator must address all questions raised by the patient. The investigator or designee will also sign the ICF.

The SOA is presented in [Table 6-1](#). Detailed instructions for study site activities will be provided in the study manual.

Table 6-1 Schedule of Study Site Activities

Activity	Screening	Treatment Period										Follow-Up Period				
	Time Point	Day -28	Day -1	Day 1	Week 1	Week2	Week 3	Week 5	Week 7	Week 9	Week 12	Week 16	Week 20	Week 24	Week 38	Week 52
Visit Window (Day)	-28 to -7	-	-	5-9	12-16	18-24	32-38	46-52	60-66	81-87	105-119	133-147	161-175	259-273	357-371	
Visit No.	Visit 1	Visit 2	Visit 3	Visit 4	Optional Visit	Visit 5	Visit 6	Visit 7	Visit 8	Visit 9	Visit 10	Visit 11	Visit 12	Visit 13	Visit 14	
Informed consent	X															
Demographics	X															
Medical history and concomitant disease	X	X ^a														
Physical examination and vital sign measurements	X									X						
Urine drug screen	X															
Urine pregnancy test (if applicable)		X ^a									X					
Laboratory sampling	X									X						
Eligibility evaluation	X	X ^b														
Descemetorhexis with photo or video documentation		X														
Randomisation		X														
Dispense study drug			X	X		X	X	X	X	X						
study drug ^c				X	(X) ^d	X	X	X	X	X	X					
Study drug administration			X	X	(X) ^d	X	X	X	X	X						
Slit-lamp evaluation	X	X ^a	X	X	(X) ^d	X	X	X	X	X	X	X	X	X	X	
Corneal ECD measurement ^e (specular microscopy, non-contact type)	X			X	(X) ^d	X	X	X	X	X	X	X	X	X	X	
Corneal ECD measurement by HRT ^f	(X)			(X)	(X) ^d	(X)	(X)	(X)	(X)	(X)	(X)	(X)	(X)	(X)	(X)	

Activity	Screening	Treatment Period										Follow-Up Period				
	Time Point	Day -28	Day -1	Day 1	Week 1	Week2	Week 3	Week 5	Week 7	Week 9	Week 12	Week 16	Week 20	Week 24	Week 38	Week 52
Visit Window (Day)	-28 to -7	-	-	5-9	12-16	18-24	32-38	46-52	60-66	81-87	105-119	133-147	161-175	259-273	357-371	
Visit No.	Visit 1	Visit 2	Visit 3	Visit 4	Optional Visit	Visit 5	Visit 6	Visit 7	Visit 8	Visit 9	Visit 10	Visit 11	Visit 12	Visit 13	Visit 14	
BCVA (ETDRS scale)	X			X	(X) ^d	X	X	X	X	X	X	X	X	X	X	
Corneal thickness (ultrasound pachymeters)	X			X	(X) ^d	X	X	X	X	X	X	X	X	X	X	
Corneal morphology (Pentacam or Orbscan)	X			X	(X) ^d	X	X	X	X	X	X	X	X	X	X	
Contrast sensitivity ^f (CSV-1000 chart)	X			X	(X) ^d	X	X	X	X	X	X	X	X	X	X	
Intra-ocular pressure (contact or non-contact type tonometer)	X		(X) ^g	X	(X) ^d	X	X	X	X	X	X	X	X	X	X	
██████	X						X			X			X		X	
Photo documentation of ocular findings	X			X	(X) ^d	X	X	X	X	X	X	X	X	X	X	
Concomitant therapy	X	X	X	X	(X) ^d	X	X	X	X	X	X	X	X	X	X	
Adverse event documentation		X	X	X	(X) ^d	X	X	X	X	X	X	X	X	X	X	

Abbreviation: HRT, Heidelberg retina tomography; ██████████ ██████████

- ^a Pre-operative.
- ^b Post-operative.
- ^c Both ██████████ study drug ██████████ will ██████████ and ██████████ will be recorded in the eCRF. Morning/night and mid-day/evening drug will ██████████ separately. At the optional Week 2 visit, a patient's study drug will ██████████ returned to the patient. At Visit 10, study drug ██████████ from the drug tapering phase (Week 12 through Week 14) will ██████████.
- ^d Week 2 is an optional visit (at the discretion of the investigator), but if this visit is applied, all marked assessment items must be conducted.
- ^e The study eye must be measured at all indicated visits, whereas the non-study eye must be measured only at Visit 1 and Visit 14.
- ^f Only at sites where equipment is available.
- ^g If investigator judges it necessary.

6.1 Eligibility Assessments and Procedures

6.1.1 Medical History, Physical Examination, and Laboratory Assessments

Medical history and assessments of concomitant disease, physical examination and vital sign measurements, urine screening for drugs of abuse, pregnancy screening for patients of childbearing potential, and clinical laboratory assessments will be conducted at screening primarily to assess eligibility to participate in the study. The limited physical examination includes a review of the patient's medical and medication history and subsequent evaluation of relevant body system complaints. In case of relevant findings, full evaluation of the condition needs to be conducted. Demographics information will be collected at screening as follows: age, race, iris colour, and sex.

6.1.2 Descemetorhexis of the Study Eye

Each patient will undergo descemetorhexis of the investigator-selected study eye at Visit 2 (Day -1). A digital photo of the study eye must be taken immediately before and immediately after descemetorhexis at Visit 2. The investigator will perform descemetorhexis to remove central confluent guttae, removing an area of Descemet membrane with a diameter of [REDACTED]. The longest diameter and the shortest diameter must be recorded in the eCRF. The procedure must be recorded by video to record potential differences in technique among investigators. Also, immediately after the operation, the stripped area will be recorded by photo or video with an adjacent scale to measure the area removed. Detailed guidance for performing the study eye descemetorhexis will be provided in the study manual.

Recommended post-descemetorhexis concomitant therapy is described in Section 5.8.1.

6.2 Efficacy Assessments

6.2.1 Corneal Endothelial Cell Density Measurement

6.2.1.1 Non-Contact Specular Microscopy

Corneal ECD will be measured by non-contact specular microscopy. The study eye must be assessed at all study visits as indicated in Table 6-1, whereas the non-study eye must be measured only at Visit 1 and Visit 14. The same instrument must be used for all study visits

for a given patient throughout the study. All specular microscope images taken will be sent to the [REDACTED] for analysis via a designated portal site. Please see the study manual for detailed instructions.

6.2.1.2 Heidelberg Retina Tomography

Heidelberg retina tomography (HRT) of the study eye will be performed according to the schedule in [Table 6-1](#) if the necessary equipment is available at the study site before the start of the study at that site. All HRT images taken will be sent to the [REDACTED] for analysis via a designated portal site. Please see the study manual for detailed instructions.

6.2.2 Corneal Thickness

Corneal thickness of the study eye will be measured by contact ultrasound pachymetry on the central cornea. The same instrument must be used for all study visits for a given patient throughout the study. From a safety perspective, the corneal thickness of both eyes must be measured, and the results must be recorded. See the study manual for detailed instructions.

6.2.3 Corneal Oedema

Corneal oedema of the study eye will be categorised by epithelial, stromal, or endothelial, and assessed by the investigator as either present or absent.

6.2.4 Corneal Morphology

Corneal morphology of the study eye will be assessed by OCULUS Pentacam[®] or Bausch and Lomb Orbscan[®]. If the site has both instruments, the OCULUS Pentacam will be used. The same instrument must be used for all study visits for a given patient throughout the study. All data and images must be recorded.

6.2.5 Best Corrected Visual Acuity

The BCVA of the study eye will be assessed by ETDRS testing without pupil dilation. For all measurements, the BCVA letter score will be recorded. Please see the study manual for detailed instructions on the BCVA ETDRS assessment.

6.2.6 Contrast Sensitivity

Visual contrast sensitivity of the study eye will be assessed using the VectorVision CSV-1000 instrument if the necessary equipment is available at the study site before the start of the study at that site. Please see the study manual for detailed instructions on the CSV-1000 assessment.

6.3 Safety Assessments

6.3.1 Ocular Safety Assessments

All ocular safety assessments must be performed on both eyes of each patient. Refer to the study manual for detailed instructions on each of the ocular safety assessments to be performed in this study.

The examiners must use the same mode of measurement throughout the entire study for a given patient, and the assessments must be performed by the same evaluator for a given patient.

Slit-lamp biomicroscopy will be performed at every visit using slit-lamp examination without pupil dilation to evaluate the condition of the lids, conjunctiva, anterior chamber, cornea, and lens. Additionally, digital photographs of the study eye will be taken during the slit-lamp procedure according to the study manual description. The images will be provided to the sponsor for review.

Intra-ocular pressure (IOP) may be measured by either contact or non-contact tonometry, but the same method must be used for all study visits for a given patient throughout the study and all reasonable efforts must be made to have the same examiner obtain all IOP measurements for a given subject. At each study visit, a single IOP measurement will be made for each eye, with pressure recorded in millimetres of mercury (mm Hg). The IOP measurement is at the investigator's discretion at Day 1 (Visit 3).

Ocular examination will be performed with pupil dilation using an indirect ophthalmoscope according to the current standard of practice to evaluate the condition of the vitreous, macula, retina, optic nerve, choroid, and retinal periphery.

6.3.2 Adverse Events

6.3.2.1 Definitions of Adverse Events

An AE is defined as any untoward medical occurrence in a patient enrolled into this study regardless of its causal relationship to study drug. An AE can therefore be any unfavourable and unintended sign (including an abnormal laboratory finding), symptom, or disease temporally associated with the use of a medicinal product, whether or not considered related to the medicinal product. Patients will be instructed to contact the investigator at any time after randomisation if any symptoms develop.

An AE may include the following:

- Exacerbation of a pre-existing disease or symptom
- Increase in frequency or intensity of a pre-existing event or condition
- A condition detected or diagnosed after study drug administration even though it may have been present prior to the start of the study

An AE does not include the following:

- Medical or surgical procedures (although the condition that leads to the procedure must be reported as an AE)
- Pre-planned medical procedures (eg, planned surgical interventions, investigations, social and/or convenience hospitalisations)
- Pre-existing disease or conditions present at the time of signing the ICF are considered concurrent medical conditions and must not be recorded as an AE

The investigator must attempt to establish a diagnosis of the event based on signs, symptoms, and other clinical information. In such cases, the diagnosis must be documented as the AE and not as the individual signs or symptoms.

The investigator will evaluate any changes in laboratory values and other study investigations and determine whether the change is clinically important and whether it is related to the study drug. The investigator must record the AE or investigation abnormality in the eCRF regardless of the relationship to the study drug (ie, the AE will be recorded whether or not it is considered related to the study drug).

Considerations for determining whether an abnormal objective test finding must be reported as an AE may include whether or not::

- The test result is associated with accompanying symptoms
- The test result requires additional diagnostic testing or medical/surgical intervention
- The test result leads to a change in study drug dosing or discontinuation from the study, significant additional concomitant drug treatment or other therapy and/or
- The test result leads to any of the outcomes included in the definition of an SAE

Merely repeating an abnormal test, in the absence of any of the above conditions, does not require reporting as an AE. An abnormal test result that is determined to be an error or artefact does not require reporting as an AE.

A treatment-emergent AE (TEAE) is defined as any event not present before exposure to study drug or any event already present that worsens in either intensity or frequency after exposure to study drug.

An SAE is defined as any event that

- results in death.
Any death resulting from an AE occurring during the study period or within 30 days after the last dose of the study drug, even if the death appears to be completely unrelated to the study or study drug.

- is immediately life threatening.
The term ‘life-threatening’ refers to an event in which the patient was at risk of death at the time of the event; it does not refer to an event that hypothetically might have caused death if it were more severe.
- requires inpatient hospitalisation or prolongation of existing hospitalisation.
The term ‘hospitalisation’ means a hospital admission or an overnight stay; prolongation means delay of a planned or anticipated discharge date by at least 1 overnight stay. Adverse events which require attendance at hospital but do not require admission may be considered medically important.
- results in persistent or significant disability/incapacity.
- results in impairment, damage, or disruption in the study patient’s body function or structure, or physical ability or quality of life.
- is a congenital anomaly/birth defect.
Additionally, events in which there is suspicion that exposure of either parent to the study drug resulted in an adverse outcome in the offspring is a medically important event.
- Is medically important: an event that may not be immediately life-threatening or fatal or result in hospitalisation, but may require intervention to prevent one of the serious outcomes listed above.
Examples of such events are intensive treatment in an emergency room or at home for allergic bronchospasm; blood dyscrasias; convulsions that do not result in hospitalisation; or development of drug dependency or drug abuse.

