6.3.2.3 Reporting Adverse Events

All AEs reported or observed will be recorded on the AE page of the eCRF. Information to be collected includes event term, time of onset, date of resolution of the event, seriousness, severity, relatedness to study drug, any required treatment or evaluations, and outcome.

The investigator will assess the severity of the event. The severity (intensity) of AEs must be classified using the following criteria:

- **Mild:** An AE that is easily tolerated by the patient, causes minimal discomfort, and does not interfere with everyday activities
- **Moderate:** An AE that causes enough discomfort to interfere with normal everyday activities and may require intervention
- **Severe:** An AE that prevents normal everyday activities (treatment or intervention will usually be required). Severe events are usually incapacitating

When changes in the severity of an AE occur more frequently than once a day, the maximum intensity for the event must be noted for that day. Any changes in intensity of signs and symptoms over multiple days will be captured by recording new AEs, with the amended intensity grades and the dates (and time, if known) of the change(s). Changes in the intensity

of an AE must be documented to allow an assessment of the duration of the event at each level of intensity.

The investigator will assess the causal relationship between the study medication and the AE and decide whether, in his or her qualified medical judgement, there is a reasonable possibility that the event may have been caused by the study drug. There are 2 categories of causality:

- **Unrelated:** If no valid reason exists for suggesting a relationship, or the event may plausibly be related to the patient's clinical condition, an underlying disease or other medication taken by the patient, then the AE must be considered unrelated.
- **Related:** If there is any valid reason for supposing that there is a relationship between the study medicine and the AE, especially if the event improves on withdrawal of the drug (de-challenge) or recurs on recommencement of therapy (re-challenge), then the AE must be considered related. The AE must not be considered related simply because it is not possible to rule out an association between the AE and the study drug.

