The investigator's assessment of an AE's relationship to study drug is part of the documentation process, but it is not a factor in determining what is or is not reported in the study. If there is any doubt as to whether a clinical observation is an AE, the event must be reported.

The action taken with the study medication must be recorded as treatment continued, treatment interrupted, or treatment discontinued. If the patient is no longer taking study medication at the time of the event, then action taken must be recorded as not applicable.

All AEs will be followed to adequate resolution. The Medical Dictionary for Regulatory Activities (MedDRA) will be used to code all AEs.

Any AE that meets SAE criteria (Section 6.3.2.1) must be reported to the [REDACTED] Pharmacovigilance Department immediately (ie, within 24 hours) after the time site staff first learn about the event, using the electronic data capture (EDC) system. If for any reason the EDC is not available to the study site, the following contact information is to be used for SAE reporting:

██████████ **Pharmacovigilance Department**

If the initial contact to ██████████ Pharmacovigilance is made via the SAE Hotline or the SAE fax line, the SAE must still be reported, urgently, using the EDC system when it becomes available. Details on SAE reporting are presented in the study manual.

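### One SAE criterion in protocol section 6.3.2.1 has no persistence or significance qualifier, so as written it can class non-serious events as serious and sites may apply it differently.

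*Protocol*

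**What the plan says.** Section 6.3.2.1 opens its list with "An SAE is defined as any event that" and then gives bullets, any one of which is enough. One bullet reads "results in persistent or significant disability/incapacity". The next, with its own bullet and its own verb, reads "results in impairment, damage, or disruption in the study" patient's "body function or structure, or physical ability or quality of life". It carries no word such as persistent, significant, substantial or permanent. The last bullet, on medically important events, covers an event that "may require intervention to prevent one of the serious outcomes listed above".

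Section 6.3.2.3 records seriousness and severity as separate items and defines the moderate grade as "An AE that causes enough discomfort to interfere with normal everyday activities and may require intervention". On reporting it says: "Any AE that meets SAE criteria (Section 6.3.2.1) must be reported to the" pharmacovigilance department, with a limit of 24 hours after site staff first learn of the event.

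**The concern.** Disability and impairment of function are normally one seriousness criterion with one threshold. Here they are two, and only the first has the threshold. Any event that meets the disability criterion also meets the looser one, so the qualifier has no effect.

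The looser criterion also reaches well down the severity scale. An event that interferes with everyday activities can fairly be called a disruption of physical ability or quality of life. In this trial every patient has an area of Descemet's membrane removed, and section 1 says that corneal oedema produces visual haze. Transient haze after surgery is therefore the kind of event on which two investigators could differ. One follows the bullet and files a 24-hour report. The other applies the usual sense of serious and does not. What is at stake is whether the SAE listing means the same thing from site to site.

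**Working it through.** No formula applies, because the point concerns the wording of a definition. The check sets the relevant passages side by side.

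1. **Is the bullet a criterion or an explanation of the one above?** Elsewhere in the list (death, life-threatening events, hospitalisation, congenital anomaly, medically important events) explanatory text stands as unbulleted lines under its criterion. This text has its own bullet and completes the stem of the list by itself. It is a criterion.

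2. **Does anything nearby narrow it?** Sections 6.3.2.1 to 6.3.2.5 contain no sentence that limits it or ties it to the disability bullet, and no exemption for findings expected after descemetorhexis.

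3. **Does it spread to other rules?** Yes, in two places. The medically important bullet refers back to all listed outcomes, so it takes in treatment given to prevent any impairment. Section 6.3.2.1 also names SAE outcomes among the considerations for deciding whether an abnormal test finding is an AE at all, so the loose bullet can widen AE recording too.

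4. **Does it overlap with the severity scale?** The moderate grade turns on discomfort that interferes with normal activities. That can satisfy the bullet, though the text does not say that it always does.

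5. **Could post-operative oedema or blur be caught?** Only if it is first recorded as an AE. The definition is broad: "An AE is defined as any untoward medical occurrence in a patient enrolled into this study". The exclusions are procedures and conditions already present at consent, and worsening of a pre-existing disease may count as an AE. Section 6.3.2.2 requires reporting regardless of clinical significance, and section 6.3.2.3 tells sites to report in case of doubt. Against this, oedema is also an efficacy assessment (sections 6.2.3 and 7.2), and no passage says outright that it is to be recorded as an AE.

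6. **Scale.**
   - Section 4.1 gives about 60 patients at about 30 sites: 60 / 30 = about 2 per site. Each reading of the bullet would rest on very few patients.
   - Section 7.4 assumes about 10% with cell density unmeasurable because of oedema at Week 12: 0.10 × 60 = about 6 patients.
   - Those 6 do not count the misclassified events. Oedema still present at Week 12 might qualify as persistent under the stricter bullet as well. The wording matters most for earlier, transient oedema, for which the documents give no rate.

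7. **Who would harmonise the readings?** Section 6.4 provides no safety monitoring committee, and section 11.1.1 no external data monitoring committee.

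**The case against.** The strongest case on the other side is that the list, read as a whole, points to a higher threshold. Hospital attendance without admission is only possibly medically important, and the examples given are allergic bronchospasm needing intensive treatment, blood dyscrasias and convulsions. Those lines make little sense if every moderate event were already serious, and a sensible investigator would read the two bullets together. The wording also errs on the cautious side: it costs extra reports and does not miss serious events. Finally, the study manual, which is not available here, holds further detail on SAE reporting and may already narrow the bullet.

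Much of this stands, and it limits the consequences. A reader might infer four stronger things that the documents do not support:

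- **That every moderate AE is serious.** The moderate grade is about discomfort, and seriousness is judged separately. Overlap is likely, but equivalence is an inference.
- **That the SUSAR count would be inflated.** Section 6.3.2.3 classes an event plausibly due to the patient's condition as unrelated, and section 6.3.2.4 adds an expectedness check by the sponsor. Ordinary post-operative haze should not pass both.
- **That true serious events would be hidden.** Section 7.7.4.1 makes treatment-emergent AEs the main tabulation and lists SAEs separately. An infection would still appear under its own term.
- **That one arm would be favoured.** Allocation is randomised and investigators and site staff are masked (sections 5.1 and 5.6), so different readings add noise, not a systematic difference.

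What the objection does not remove is the text. Nothing in the protocol tells an investigator to read the two bullets together, and a manual should not have to correct a protocol definition.

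**Conclusion.** The criterion is wrong as written. Followed literally, it makes the qualified disability criterion redundant and can class non-serious events as serious, each with a 24-hour report. The expected harm is modest: unnecessary reports, and an SAE listing (and SAE summary, if one is produced) that is less comparable across about 30 sites. Neither the primary endpoint nor any efficacy analysis is affected.

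The size cannot be derived. It depends on how many sites read the bullet literally and how many record transient oedema or blur as an AE, and the documents give neither. A claim that most patients would have an SAE, or that the SAE rate would change by an order of magnitude, would be a guess. The conclusion assumes that the study manual does not already qualify the bullet. If it does, the protocol and manual disagree and still need to be aligned.

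**What to change.** In section 6.3.2.1, merge the two bullets so that one qualifier governs both. The criterion would read "results in persistent or significant disability/incapacity", that is, a persistent or significant impairment, damage or disruption of "body function or structure, or physical ability or quality of life". The medically important bullet then refers back to the narrower list without further change. Carry the same text into the study manual and the SAE form.

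The cost is a wording change and a short site-training note, with no new data. SAEs already filed under the current bullet need one re-check for seriousness against a documented rule. The SAP addendum (section 1) was written after the Week 12 unmasking, so the re-check should be made by people without access to treatment assignments.
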